### **The Educational Intervention:**

The intervention will be followed by a question and answer session. The intervention will focus on phthalate reducing behaviors because of the well documented animal and human evidence on their effects on reproductive health and development, they are ubiquitous and added to HCPs to provide scent, detected in human breast milk, urine, amniotic fluid and placenta (suggesting fetal exposure) and phthalate interventions have proven successful. At the end of the intervention, we will also administer a similar Precaution Adoption Process Model Questionnaire to assess the impact of the intervention.

A trained staff member will prior to the start of the educational intervention if taking place in-person:

1. review the consent form with the participant and obtain written consent before the intervention begins
2. Administer the Sociodemographic Questionnaire (participant self-completes or if preferred, completed with interviewer) before the intervention begins.
3. Administer the Precaution Adoption Process Model Questionnaire (participant self-completes) before the intervention begins.
4. Provide the Hair Care Product Questionnaire to be self-completed if they did not complete the questionnaire prior to the session. Or, provide a return envelope if the participant forgot to bring the completed questionnaire with them.

Remote Option: A trained staff member will have gone over the consent process remotely and will send them links from Qualtrix to complete the Sociodemographic Questionnaire and the Precaution Adoption Process Model Questionnaire prior to the educational intervention.

### **The Focus Groups:**

From consumer theory, when a rational consumer is faced with a set of options, the consumer will place values or preferences to each option, and then choose the preferred. However, consumers are making decisions based on multiple attributes that determine the hair care products' utility and therefore the purchase. Therefore, while we hypothesize that our educational intervention will make participants more aware of the importance of ingredients as an HCP attribute, women will unlikely make maintainable HCP use decisions based on ingredients alone. Thus, pulling from consumer discrete decision making, we will determine what attributes WOC apply when making decisions about HCPs. Factors identified will inform a behavioral

intervention that targets educational awareness plus other attributes that participants apply to HCP use decisions.

Phase V: Follow-Up – ALL REMOTE There will be two follow-up sessions conducted over the phone that will take place about Mid-Late 3rd trimester (Follow-Up 1) and 1-month postpartum (Follow-Up 2). At each follow-up, the following will be collected: repeat Hair Care Product Questionnaire, repeat Precaution Adoption Process Model Questionnaire, and first morning urine collection.

## **Recruitment and Consent**

We will enroll n=50-100 adult pregnant women (18 years or older), who are within 0-4 weeks of the 3rd trimester of their pregnancy, speaks English and/or Spanish, and lives within Manhattan, Bronx, Queens, Brooklyn, Staten Island. We will recruit through (1) Instagram advertisements and (2) the OBGYN clinic. We have experience recruiting pregnant women through the Columbia Ambulatory Care Network for the Milk-Associated Markers And Breast Optical Spectroscopy Study (MAMA BOSS) pilot study (PI: [name], IRB# AAAR4711) which is a study designed to understand postpartum breast biology. We will be working alongside [name] [name] who is the OB/GYN director of the Ambulatory Care Network, the site director at the Rangel Community Health Center, and an admitting physician at the New York Presbyterian/Allen Hospital to recruit participants. [name] will approach potentially eligible or soon to be eligible mothers being seen at the ACN and provide them with a packet comprised of the study Consent Form and a Welcome Letter. [name] will then allow the mother time to review the packet privately and will thereafter answer any questions and obtain the name and contact information of those who might be interested in being contacted. [name] will provide the PI and research staff with the name and contact number of pregnant women who have expressed interest in the study and who have provided verbal permission to be approached by the study team for participation. The research team will then follow-up with the interested individual either by phone or by email and conduct the eligibility and enrollment process. If eligibility is confirmed, the participant will be scheduled to attend the educational intervention. Our current location for the intervention is the Community Engagement Core Community Space (affiliated with the Irving Medical Center) in Washington Heights.

We will also use the CCPH Columbia Community Partnership for Health and Community Engagement Core Resource based out of the Irving Medical Center to assist with recruitment.

Additional recruitment strategies will include:

1. We will contact the Directors and Chiefs of other Ambulatory Care Networks and Obstetrics & Gynecology Divisions here at Columbia Presbyteran and local facilities (e.g., Allen Hospital) in the CUIMC catchment area to see if we can leave fliers in the waiting areas.
2. Research flyer that will be distributed in locations throughout Manhattan, Bronx, Queens, Brooklyn, Staten Island, including but not limited to, public libraries, health food stores, coffee shops, and hospitals.

3. We also will have a short post for online local parent groups that allow postings. The post will include language as written on the flier and within the consent. Interested parties will be able to call or email us to get more information.

4. We will post the electronic version of the study flyer or a short post that includes language as written on the flyer on Craigslist, community websites, and other websites where research studies are appropriate for posting. Interested parties will be able to call or email us to get more information. For any referrals, the study coordinator will confirm eligibility by administering a short eligibility questionnaire over the phone or in-person. If eligible, a study coordinator will proceed with the consent process.

**Consent:** Once a woman has been identified as a potential participant by one of our recruitment partners, or if they reach out to us after having seen recruitment materials, they will be administered the eligibility screener questionnaire by a trained study team member (over the phone). If the participant is determined eligible, the study team member will email or text message the participant a link that takes them to the Remote Electronic Consent process on Qualtrics. The study team member will initiate the Informed Consent Process, which will begin with a concise and focused presentation of the key information about the research study. This will be accomplished by verbally reviewing the complete consent form with the participant (25-30 minutes) on the phone. In the beginning of the Informed Consent Process, the study team member will obtain verbal consent to share the study materials with the participant, either mailed or electronic. Mailed study materials would include a urine collection kit with instructions. Electronic study materials would include a link to the electronic version of this consent form, questionnaires, biospecimen collection forms, and study reminders. The participant can select from one of the following options:

1. Consent to having the study materials mailed to the address the participant provides
2. Consent to having the study materials e-mailed to the email address the participant provides
3. Consent to having the study materials texted to the cell phone number the participant provides
4. Not consenting to having study materials mailed or electronically sent. In the case of option 4, the study personnel will explain to them that it will be difficult for them to participate in this study remotely. Study personnel then read the participant the following, “If, and when, this study has an in-person component, may we contact you in the future? This will be the end of the consent process for this study. Thank you!” and the participant can answer “yes” or “no.” This will be the end of the consent process for this study.

The verbal consent obtained by the study staff from the participant is only so they can send the participant the study materials. They will also receive (via text or email) a link to the remote e-consent process administered on Qualtrics. They will provide written consent that applies to the entire study via the e-consent process administered on Qualtrics. Please note- the urine collection (biospecimen) process is not part of the screening process; participants are only asked to provide urine samples once they have consented to participate in the study.

In the case verbal consent is granted, the following options will ensue: If the study takes place in-person for the intervention or focus group, we will have obtained verbal consent, but will also obtain written consent at that time. We will provide the participant a copy of the signed consent form in person.

If the entire study takes place remotely, and the participant completes the remote E-Consent process at the time of consenting, a copy of the consent will be generated and emailed to the participant and available to them for the duration of the study. We will also, upon request, send a hard copy to the participants address.

In both cases, written consent will be obtained for the entirety of the study.

If the entire study takes place remotely, and the participant was unable to complete the E-Consent at the time of the phone call, we will ask the participant to e-consent at a later date and send reminders up until the day of the session. If the participant has chosen to consent through a hard copy, we will send the consent to an email address and to the provided address with a return email address and a pre-paid envelope to return via mail. If the participant does not econsent or provide written consent via email or mail, they will not be permitted to participate in the session.

Emails/texts will be sent by a Columbia Research team member through Outlook, Mailchimp or Qualtrics (or SMS if using study cellphone to text) and will include a link to a Qualtrics survey, which includes the e-Consent form. Written consent for the entire study will be obtained.

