Hair care products (HCPs) are a class of personal care products (PCPs) that contain EDCs; there are stark differences in HCP use by race (6,14-17). In a group of racially and ethnically diverse women (n=301), compared to non-Hispanic white women, women of African descent were more frequent users of hair oils, lotions, leave-in conditioner, root stimulator and perm/relaxers (14). The Sister Study has also shown where 67% of Black women were users of hair pomades and straighteners, only 3% of White women were users (7). Differences in hair texture may explain differences in use. Nevertheless, of major concern, clinical, epidemiological, and laboratory studies have suggested HCPs are associated with earlier pubertal events, (6,18-21) where the timing of pubertal maturation is an established risk factor for BC risk (22-24). Additional studies have shown that compared to infrequent users, women classified as moderate or frequent users of PCPs had a 10-15% higher BC risk,(25) dark hair dye is associated with a 52-72% increased BC risk, (17,26) a history of chemical relaxer or straightener use is associated with a 64-74% increase in BC risk, (17,27) and in 454 Mexican women (233 cases) urinary concentrations of monoethyl phthalate (MEP) were positively associated with BC [OR 2.2. (1.33, 3.63)], with stronger associations observed for pre-menopausal women [OR 4.1. (1.6, 10.7)] (28).

Evidence is emerging on EDC exposures across the pregnancy/postpartum periods. This is of importance because while pregnancy is associated with a long-term reduced risk of BC, it also confers an increased risk of BC for at least a decade after birth (1,2,8,9). EDC exposure during this period of increased risk could promote ‘activation’ effects for BC following pregnancy. In pregnant women, PCP use is correlated with higher concentrations of urinary phthalates, (29-31) urinary metabolite concentrations vary by PCP type,(32,33) and urinary metabolite concentrations differ by sociodemographic factors and across racial and ethnic populations (34). For example, a multiethnic cohort of 446 pregnant women found that urinary phthalate metabolites were significantly higher among WOC (34). However, while studies assess knowledge and attitudes of PCPs during the pregnancy/postpartum periods, no study has implemented a behavioral intervention. Five cross-sectional studies have examined knowledge,

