## **Study Design**

### **Objective:**

To reduce use of personal care products that contain endocrine disrupting chemicals among women. For this pilot intervention, we focus on the hair care product class of personal care products, the reduction in use of phthalate-containing Hair Care Products (HCPs) and use among pregnant Women of Color (WOC).

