## **Procedures**

**Objective:** To reduce use of personal care products that contain endocrine disruptor chemicals among women.

The below details the Pilot Intervention

**Study Overview:** To reduce use of phthalate-containing hair care products among women of color. We will apply the Precaution Adoption Process Model (PAPM).

All activities will be performed remote or in person based on IRB mandates. We will submit Questionnaires and Facilitator Forms after initial IRB protocol approval.

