## **Specific Aims:**

1. Qualitative Approaches across 5 groups (n=50-100 total participants), we will:

- a. Deliver an educational intervention on harmful chemical exposures, such as phthalates, found in hair care products, developed by the research team using empirical evidence with key informant feedback.
- b. Through focus groups gather participant feedback on content and questions pertaining to intervention and attributes women of color consider when deciding on hair care product use, using a semi-structured guide.

2. Quantitative Approaches using repeat measures, we will:

- a. Using repeated questionnaires to assess PAPM stages, we will assess self-reported behavioral changes in the use of phthalate-free hair care products comparing stage at enrollment to:
  - Stage after the intervention (post-test1),
  - Stage at 1-month post-intervention (post-test2), and
  - Stage at 1-month postpartum (post-test3).
- b. Examine the correlation between self-reported behavioral change assessed by the PAPM questionnaire and
  - Change in self-reported HCP exposure measured via questionnaire (n=50),
  - Change in internal dose of urinary phthalate metabolites (targeted gas chromatography/high resolution mass spectrometry (GC/HRMS) Orbitrap; n=25 with 3-repeat samples),

- (Exploratory) change in internal dose of all-other detectable urinary metabolites (untargeted GC/HRMS-Orbitrap; n=25 with 3-repeat samples).

Questionnaire Constructs : All who wish to enroll and who enroll in the study will be asked to complete the following questionnaires which will be administered preferably via Qualtrix but in paper format if requested.

Eligibility Questionnaire: Confirm that potential participants meet the eligibility requirements (Black or Hispanic women, residing in Northern Manhattan and in the 3rd trimester of pregnancy).

Sociodemographic Questionnaire: Information that includes maternal age, gestational age, race/ethnicity, occupation and educational attainment, and reproductive characteristics and pregnancy details.

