**Phase II: Recruitment, Enrollment, Consent, and Retention** Please see the “Recruitment and Consent” section of the protocol for details. In brief, we will check for participant eligibility, enroll, and consent 50-100 women of color within Northern Manhattan who are early in their 3rd trimester of pregnancy and speak English and/or Spanish.

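### Women who enter and stay at the top adoption stage are coded as stagnant alongside women who did not respond, and Aim 2 gives no result restricted to women who can still progress or reduce use

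*Combined protocol and SAP*

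**What the plan says.** The Study Overview under Procedures gives the purpose: "To reduce use of phthalate-containing hair care products among women of color". Eligibility is described in several places. Recruitment and Consent says "We will enroll n=50-100 adult pregnant women (18 years or older), who are within 0-4 weeks of the 3rd trimester of their pregnancy", followed by language and residence in the five boroughs. The Eligibility Questionnaire entry checks for "Black or Hispanic women, residing in Northern Manhattan and in the 3rd trimester of pregnancy". Phase II describes women "early in their 3rd trimester of pregnancy and speak English and/or Spanish". Study Aims repeats race or ethnicity, residence and trimester. These statements differ on residence, but none mentions hair product use or PAPM stage.

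Aim 2b sets n=50 for change in self-reported exposure and n=25, with three samples each, for urine. Neither number is tied to baseline use or stage.

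The PAPM Questionnaire section classifies movement between assessments as progresses, regresses or stagnant. Movement to Stage 4 gets its own label (negative progresses). There is no corresponding rule for Stage 7, the highest stage, which means regular use of phthalate-free products. The Metabolomics section then fills the urine sample by giving priority to women with three samples who are classed as progresses or stagnant from post-test1 to post-test3.

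The PAPM pre-test and the Hair Care Product Questionnaire are both scheduled before the education.

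**The concern.** Two groups of women have no room to move on one of the Aim 2 outcomes.

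- **Pre-test Stage 7.** No stage lies above it, so such a woman can only be stagnant or regress. Maintaining the behaviour the study wants receives the same code as never responding to the education.
- **No phthalate-containing product at baseline.** Such a woman can only stay at zero or rise.

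If either group is sizeable, all-women summaries partly describe who enrolled and not only what the education did. The urine comparison has a further problem: its stagnant group can mix regular phthalate-free users with women who changed nothing, which blurs the contrast with the progresses group.

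**Working it through.** **No plan figure to reproduce.** The documents state n=50-100, n=50 and n=25 without alpha, power, effect size or standard deviation (SD). The values below are assumptions used to show the size of the effect.

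**Step 1. Keep the groups apart.** Let f7 be the share at pre-test Stage 7 and f0 the share with no phthalate-containing product at baseline. They are not the same women. A non-user at Stages 1-6 can still progress. A Stage 6 woman, who has used a phthalate-free product at least once, may still use phthalate-containing ones and reduce them. The documents give neither share, so 10%, 20% and 33% are assumed for each.

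**Step 2. Progress share.** Observed progress = (1-f7) × progress among women who can progress. With an assumed 50%:
- f7 = 10%: 0.90 × 50% = 45%
- f7 = 20%: 0.80 × 50% = 40%
- f7 = 33%: 0.67 × 50% = 33.5%

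**Step 3. Mean reduction in use.** If women with none stay at zero, the observed mean = (1-f0) × mean among users. An assumed 0.50 SD becomes 0.45, 0.40 and 0.335 SD. If some of them rise, it is smaller still.

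**Step 4. Women able to move, n(1-f).** For n=50: 45, 40 and 33.5. For n=25: 22.5, 20 and 16.75.

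**Step 5. Spearman correlation of stage movement with change in use.** This was simulated with 200,000 records, assuming 50% progress, 15% regress, a mean reduction of 0.5 SD and a latent correlation of 0.5 or 0.3 between progress and reduction. A share f is then given zero change in use.

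| Latent correlation | Who the share f are | f=0 | 10% | 20% | 33% |
|---|---|---|---|---|---|
| 0.5 | Stage 7, stagnant | -0.43 | -0.46 | -0.46 | -0.48 |
| 0.5 | Non-users who still move through stages | -0.43 | -0.40 | -0.36 | -0.32 |
| 0.3 | Stage 7, stagnant | -0.26 | -0.28 | -0.31 | -0.32 |
| 0.3 | Non-users who still move through stages | -0.26 | -0.23 | -0.22 | -0.19 |

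Stage 7 stayers add points at no movement and no change, which sharpens the apparent link. Non-users who move add stage movement with no change in use, which weakens it. The planned correlation of pre-test with post-test stage is also affected: women who stay at Stage 7 add agreement that owes nothing to the education.

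**Step 6. Cost in precision.** Take n=50 with 20% unable to move and 20 women progressing. The restricted result is 20/40 = 50% (Wilson 95% interval 35-65%). The all-women result is 20/50 = 40% (28-54%).

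**Step 7. Why baseline use should stratify and not select.** The product questionnaire is described as built on a list of products used in the last 24-48 hours. Suppose similar users with mean use m, no true change, and independent recall windows, and let a share p0 list nothing by chance. Women listing at least one product then average m/(1-p0) at baseline and m later, a spurious fall of p0; p0 = 20% gives a 20% apparent reduction. Women listing none rise from 0 to m. The all-women mean is unaffected.

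**The case against.** The strongest reply is that an all-women denominator is legitimate for an unpowered pilot of education in an open population. Aim 1 and the awareness hypothesis do not need product users, and a non-user below Stage 7 can still progress. That stands, and it is why no entry criterion is proposed.

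A second reply is that the plan already has descriptive statistics by pre-test, by post-test and by PAPM category, and product frequencies by category and overall. These would show how many women start at Stage 7 or with no such product. They do not give progress or change among women able to move, and they do not separate Stage 7 stayers from other stagnant women.

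Several stronger readings are tempting but not supported:

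- **That women with no room to improve always pull results towards no effect.** This holds for progress shares and mean reductions. Step 5 shows that it does not hold for the planned correlations.
- **That the share is known to be large.** The Background figure, "67% of Black women were users of hair pomades and straighteners", comes from another cohort and concerns two product types, not phthalate content or PAPM stage. Flyers in "public libraries, health food stores, coffee shops, and hospitals" are one additional strategy; the main routes are Instagram and the OBGYN clinic. The plan also calls phthalates ubiquitous, which points towards few non-users.
- **That the pilot would mis-size or misdirect the later intervention.** No passage says the Aim 2 results will size a later trial. The Focus Groups section bases the later intervention on product attributes identified in Aim 1.
- **That baseline users should be the primary analysis set.** Step 7 shows that such selection can create an apparent reduction, with no control group to expose it.

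**Conclusion.** The point holds in a limited form. Eligibility ignores product use and stage, the classification has no rule for women who enter and stay at Stage 7, and the urine selection carries that coding forward. All-women progress shares shrink by the factor 1-f7. Mean reductions shrink by 1-f0 if non-users stay at zero. At the assumed 10%, 20% and 33%, a true 50% progress is seen as 45%, 40% and 33.5%. The correlations can be strengthened or weakened, depending on which group is present.

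These sizes rest on assumed shares and an assumed 50% progress; the correlation figures also rest on the simulation's assumptions. No figure stated in the plan is wrong. This is an inexpensive improvement in reporting and not a defect in enrollment.

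**What to change.** Keep enrollment open and keep the all-enrolled results. Add the following to the analysis text, using forms already collected before the education:

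1. Code women at pre-test Stage 7 who remain there as a separate category, maintained, and not as stagnant. Apply the same coding in the Metabolomics selection, so that the stagnant women given priority do not include them.
2. Report progress among women at pre-test Stages 1-6, and adoption (reaching Stage 6 or 7) among women at pre-test Stages 1-5. Give the number excluded from each, and keep the plan's separate label for movement to Stage 4.
3. Show change in phthalate-containing product use by baseline use (any versus none) next to the all-women result and not in place of it. Define baseline use from the questionnaire's current or recent use, not only from a 24-48 hour list. State that regression to the mean can affect both strata in a single-arm design.

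The cost is analysis wording, with no new visit, form or assay. The downside is smaller denominators and wider intervals: with 40 instead of 50 women in the example above, the interval is about 30 percentage points wide (35-65%) instead of about 26 (28-54%).
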